6.8.2 Reactions During Build-up Phase: Preventative and Non-pharmacological Interventions

The process algorithm for symptoms during the build-up/up-dosing phase is shown in **Figure 6–2.**

Subjects will begin the Clinical Research Center dosing scheme as outlined until 300 mg/day of peanut protein is reached. Subjects will return for a supervised dose escalation in the clinic every 2 weeks. It is advised that subjects be called the morning of the day after each dose escalation visit to assess for delayed or biphasic allergic reactions. Subjects will be called 1 week after each dose escalation visit to assess for dosing compliance and dose reactions. Any dose escalation attempts may be postponed for 1-2 extra weeks based on clinical judgment. An escalation attempt must be made by 4 weeks. Subjects should withhold their daily home dose on the escalation day but should take all other prescribed medications. Note that the daily home dose should be taken as part of a meal. It is recommended that the dose be taken at a consistent time (within a 4-hour time period), and it is critical to take the dose every day. Doses should be separated by at least 12 h.

Subjects who require dosing reduction during the 2-week period will reset their 2-week escalation schedule to maintain the new dose for a 2-week period prior to attempting to escalate again.

With the occurrence of symptoms of a dose-reaction or any allergic reaction, subjects/parents (or guardians) are instructed to call the study site.

Should significant systemic symptoms, which may include mild symptoms based on physician discretion or moderate or greater symptoms, be reported during the daily home dosing, the symptom/dosing algorithm will be followed (see Figure 6–2) to determine the best course of action. The appropriate treatment will depend on the type and severity of symptoms (see Section 6.8.3).

If significant symptoms occur consistently following three attempts to increase the daily oral dose in the Clinical Research Center or clinic with each attempt spaced 2-4 weeks apart, dosing escalation will be halted at the last tolerated dose and the subject will be considered an escalation failure. These subjects will be followed for safety biweekly (following their established visit schedule) while continuing to be dosed at their last tolerated dose level until Week 24, i.e., a maintenance phase (See also Section 6.8.4). Dosing will be stopped after the Week 24 Visit; and the subject will be asked to return to the Clinical Research Center 14 days following their last dose of study product to undergo an Early Discontinuation Visit (see Section 6.5). For subjects who halt dose-escalation after Week 24, there will be no maintenance phase. Dosing in these subjects will be discontinued when dose-escalation is stopped. They will be asked to return to the Clinical Research Center 14 days following their last dose of study product to undergo an Early Discontinuation Visit (see Section 6.5). No additional DBPCFC will be performed.

Subjects will be free from active wheezing or a flare of atopic dermatitis prior to any dose escalation. Subjects will be maintained on their current dose of study product until their flare of asthma or atopic dermatitis resolves.

Subjects will be cautioned against activities likely to increase reactivity (e.g., exercising or taking hot showers or baths within 4 h after dosing).

At the physician's discretion, temporary dose reductions, ranging from a 1-step decrement (i.e., to the previous dose) to approximately half of the current dose level (to the nearest feasible available whole dose), can be instituted while subjects are suffering from symptoms of an upper respiratory infection or influenza, or during menses. If the dose is reduced by more than 1 step or for more than 3 days, the subject is to return to the CRC within 7 days of the dose-reduction for dose re-escalation under direct observation. If the reduction in dose is maintained for ≤ 3 days, then the pre-reduction dose may be resumed directly. For dose reductions of 1 dose level maintained for ≤ 3 days, whether dose re-escalation is to occur at home or in the CRC is at the investigator's discretion. If the reduction in dose is maintained for ≥ 3 days, the subject will have his or her 2-week escalation schedule reset to maintain the new dose for a 2-week period prior to re-escalating in a bi-weekly stepwise fashion.

Doses may also be withheld at the investigator's discretion, in response to an AE, whether the AE is assessed to be treatment-related or not. If doses are withheld for this, or any, reason, the rules for missed peanut OIT doses (Section 6.7) apply.

Subjects may develop symptoms during dosing for the build-up phase. The investigator's judgment will be required to determine the best course of action with possible actions being the following:

- Continue with daily home dosing
- Continue the same daily dose for the rest of the 2-week interval, with 50% of the dose split between doses given 8-12 h apart
- Return for repeat dosing in Clinical Research Center

- Return for dosing of previously tolerated dose (without escalation) in Clinical Research Center
- Discontinuation of dosing

If a subject has a dose escalation in the Clinical Research Center without symptoms, the action should be to continue per protocol with daily home dosing of the tolerated dose with the next escalation visit to the Clinical Research Center 2 weeks later.

If the subject experiences only oral/pharyngeal pruritus during the administration of the daily dose, then the same dose can be repeated the next day at home and continued throughout the interval unless other symptoms begin to develop (see below).

For *mild symptoms*, defined as:

- Skin limited (few) or localized hives, swelling (e.g., mild lip edema), skin flushing (e.g., few areas of faint erythema) or pruritus (mild, e.g., causing occasional scratching)
- Respiratory rhinorrhea (e.g., occasional sniffling or sneezing), nasal congestion, occasional cough, throat discomfort
- GI mild abdominal discomfort (including mild nauseas), minor vomiting (typically a single episode) and/or a single episode of diarrhea

The action should be either to repeat the dose the next day (Day 2) at home or to have the subject return to the Clinical Research Center the next day (Day 2) for a repeat of the previous day's dose or the last tolerated dose (at the physician's discretion). If the dose is tolerated, then the subject will continue on that dose and return at the normal interval. If the dose causes mild symptoms again, then the subject will return to the Clinical Research Center (Day 3) and be given the last tolerated dose (i.e., a 1-step dose reduction) or a 2-step dose reduction. If tolerated, the subject will continue on this dose for the normal time interval. If mild symptoms recur, a further 1-2-step reduction should be administered the next day (Day 4) in the CRC. If tolerated then that dose should be continued for 2 weeks. If not tolerated, revert to a lower dose.

If *moderate symptoms* occur, defined as:

- Skin systemic hives (e.g., numerous or widespread hives), swelling (e.g., significant lip or face edema), pruritus causing protracted scratching, more than a few areas of erythema or pronounced erythema
- Respiratory throat tightness without hoarseness, persistent cough, wheezing without dyspnea
- GI persistent moderate abdominal pain/cramping/nausea, more than a single episode of vomiting and/or diarrhea

The action should be to have the subject return to the Clinical Research Center the next day (Day 2) for dosing with the previous day's dose or the last tolerated dose (at the investigator's discretion) under observation. If the dose is tolerated, the subject will continue on that daily home dose for the normal time interval per protocol. If the subject does not tolerate this dose, the subject should receive the last tolerated dose (i.e., a 1-step

dose reduction) or a 2-step dose reduction as their next day's dose (Day 3) in the Clinical Research Center. If this dose is tolerated, it will be continued as the daily home dose for the normal time interval, then escalation attempted in the Clinical Research Center as noted below. If this dose is not tolerated, then the next dose will be a further 1-2-step reduction in dosing (per investigator judgment), and the dose will be given in the Clinical Research Center (Day 4). If this next dose is not tolerated, then a discussion with the Medical Monitor will ensue to make a decision about whether to continue the subject on study-product treatment in the study.

If more *severe symptoms* occur, defined as:

- Skin severe generalized urticarial/angioedema/erythema
- Respiratory laryngeal edema, throat tightness with hoarseness, wheezing with dyspnea, stridor
- GI significant severe abdominal pain/cramping/repetitive vomiting and/or diarrhea
- Neurological change in mental status
- Circulatory clinically significant hypotension (see Appendix 3).

The action should be to treat the subject, and at the physician's discretion either 1) have them return to the Clinical Research Center the next day (Day 2) for dosing with a 2-step reduction in dose under observation or 2) discontinue them from the study product treatment. If the subject tolerates the dose reduction, then they will remain on that dose for 2 weeks and then return to the Clinical Research Center for the dose escalation. A discussion with the Medical Monitor may ensue to make a decision about whether to continue the subject on study product treatment in the study.

If a subject fails dose escalation after three consecutive attempts (with 2-4 weeks between), he/she will be considered an escalation failure and the last tolerated dose will be accepted as the maintenance dose (to Week 24). If the dose escalation is completed with no symptoms, subjects should be observed for 30 min. If the subject exhibits mild symptoms, the duration of the observation period should be 1-2 h post-protocol. For moderate to severe symptoms, the observation period should be at least 4 h and up to 24 h based on symptoms and the treatment regimen needed to stabilize the subject's condition.

Any subject deemed to have severe symptoms including hypoxia, hypotension, or change in mental status (stage 3 anaphylaxis defined in **Appendix 3**) or who receives aggressive therapy (to be determined by the investigator, but may include such interventions as IV epinephrine, intubation, or admission to an intensive care unit) for an allergic reaction at any time should be discussed with the Medical Monitor and discontinued from study product therapy.

For specific questions related to dosing escalation or continuation of the same dose that are not answered in the above protocol, the Medical Monitor will be available for questions.

Any subject who discontinues build-up dosing due to repeated allergic reactions to the characterized peanut allergen will have his/her mechanistic blood draw (refer to **Section 8**) within approximately 1 week of discontinuation of therapy.

6.8.3 Treatment for Reactions During the Build-up Phase: Pharmacological and Supportive Treatments

Treatment of individual reactions should be with either an antihistamine and/or epinephrine, along with IV fluids, a beta-agonist (e.g., albuterol, by inhaler or nebulizer), oxygen, and glucocorticosteroids, as indicated. Generally, for mild symptoms requiring treatment, the subject should receive antihistamines. Generally, for moderate symptoms requiring treatment, the subjects should receive antihistamines and/or epinephrine, as indicated. If severe anaphylaxis (stage 3 anaphylaxis defined in **Appendix 3**) occurs at any time, dose escalation will stop and the dose will be reduced to the last tolerated dose and the subject continued on that dose as long-term maintenance without further escalation.

Antihistamines

If a subject receives antihistamines only, the dose escalation can be continued. If symptoms during a build-up day require antihistamines in multiple doses (>2) or in combination with other medications (except epinephrine), there should be a dose reduction by 1-2 doses with the next dose given in the CRC. If epinephrine is administered, then a different course of action is to be taken (see below). If dose escalation fails or requires treatment after two more escalation attempts, each spaced 2 to 4 weeks apart, the dose should be reduced to the last tolerated dose and continued long term (to Week 24) without further escalation. The subject will be followed for safety biweekly (following their established visit schedule) while continuing to be dosed at their last tolerated dose level until Week 24, i.e., a maintenance phase (see also Section 6.8.4). Dosing will be stopped after the Week 24 Visit; and the subject will be asked to return to the Clinical Research Center 14 days following their last dose of study product to undergo an Early Discontinuation Visit (see Section 6.5). For subjects who halt doseescalation after Week 24, there will be no maintenance phase. Dosing in these subjects will be discontinued when dose-escalation is stopped. They will be asked to return to the Clinical Research Center 14 days following their last dose of study product to undergo an Early Discontinuation Visit (see Section 6.5). No additional DBPCFC will be performed.

Epinephrine - General

Any reaction (in clinic or at home) that requires two or more doses of epinephrine will halt further dose escalation for this individual. Maintenance on the last tolerated dose is to be continued until Week 24. Dosing will be stopped after the Week 24 Visit; and the subject will be asked to return to the Clinical Research Center 14 days following their last dose of study product to undergo an Early Discontinuation Visit (see Section 6.5). For subjects who halt dose-escalation after Week 24, there will be no maintenance phase. Dosing in these subjects will be discontinued when dose-escalation is stopped. They will

be asked to return to the Clinical Research Center 14 days following their last dose of study product to undergo an Early Discontinuation Visit (see Section 6.5).

Epinephrine - Clinic

If a single administration of epinephrine is required during escalation in the clinic, the dose of study medication is to be reduced by two increments, or to the last tolerated dose (at the physician's discretion), and dose escalation is to continue.

If a single administration of epinephrine is required a second consecutive time during this escalation attempt, the dose should be reduced by two doses, and the subject continued on that dose for 6-8 weeks. After 6-8 weeks at the reduced dose, an escalation attempt may be tried in clinic.

If a single administration of epinephrine is required a third consecutive time during this escalation attempt, the dose should be reduced by two doses and the subject continued on that dose as long-term maintenance (to Week 24) without further escalation. (Note: an event requiring 3 consecutive administrations of epinephrine is to be reported within 24 hours of its occurrence, see Section 7.1 and 7.7.2). The subject will continue to be followed for safety biweekly (following their established visit schedule) while continuing to be dosed at their last tolerated dose level until Week 24. Dosing will be stopped after the Week 24 Visit; and the subject will be asked to return to the Clinical Research Center 14 days following their last dose of study product to undergo an Early Discontinuation Visit (see Section 6.5). For subjects who halt dose-escalation after Week 24, there will be no maintenance phase. Dosing in these subjects will be discontinued when dose-escalation is stopped. They will be asked to return to the Clinical Research Center 14 days following their last dose of study product to undergo an Early Discontinuation Visit (see Section 6.5). No additional DBPCFC will be performed.

Epinephrine - Home

If a single administration of epinephrine use occurs during dosing at home, this epinephrine use is not counted as one of the uses described above, unless severe anaphylaxis is assessed to have occurred at home. The subject should return to clinic for an observed dose prior to resuming any dosing at home.

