6.4.2 Up-dosing/Escalation visits (Up to 34 weeks post-Visit 01)

The following procedures are scheduled for the up-dosing phase, which will last approximately 24 weeks).

- Return to clinic every 2 weeks for up-dosing up to a maximum of 300 mg daily dose. The first dose of study product will be administered at the clinic.
- Concomitant medications
- Physical exam, including weight and height
- Vital signs (blood pressure, pulse rate, body temperature)
- PEFR (3 attempts are to be performed, and the best value taken). PEFR should be measured at the same time for each visit assessment.
- Return unused capsules to the clinic at each visit
- Take home capsules for daily dosing until next visit
- Monitoring for compliance and allergic symptoms (phone contact 1 week after each escalation visit)
- Adverse events monitoring

Subjects should not take their daily maintenance dose on the day of the clinic visits. The initial up-dose is to be administered at the clinic.

Subjects who require dosing reduction during the 2-week period will reset their 2-week escalation schedule to maintain the new dose for a 2-week period prior to attempting to escalate again. The procedure for setting the new, lower, dose is outlined in Section 6.8.2 and depends on the severity of the dose-related symptoms. Any dose escalation attempts may be postponed for 1-2 extra weeks based on clinical judgment. An escalation attempt must be made by 4 weeks, unless escalation is to be delayed further due to administration of epinephrine as defined in Section 6.8. Failure to successfully escalate for three consecutive attempts will result in the subject being considered an escalation failure and dose escalation will be halted at the last tolerated dose level. These subjects will be followed for safety biweekly (following their established visit schedule) while continuing to be dosed at their last tolerated dose level until Week 24, i.e., a maintenance phase (see also Section 6.8.4). Dosing will be stopped after the Week 24 visit; and the subject will be asked to return to the Clinical Research Center 14 days following their last dose of study product to undergo an Early Discontinuation Visit (see Section 6.5). For subjects who halt dose-escalation after Week 24, there will be no maintenance phase. Dosing in these subjects will be discontinued when dose-escalation is stopped. They will be asked to return to the Clinical Research Center 14 days

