- Miss 1 dose The next dose would be the current dose and could be given at home
- Miss 2 doses in a row The next dose would be the current dose and could be given at home
- Miss 3 doses in a row The next dose would be the current dose and would be given under observation (Clinical Research Center)
- Miss 4 doses in a row The next dose would be the current dose and would be given under observation (Clinical Research Center)
- Miss 5-7 doses in a row –Initiate the next dose as approximately 25% of the last tolerated dose. This would be done under observation (Clinical Research Center). Dose escalation would occur in the Clinical Research Center with an escalation no sooner than weekly and no longer than every 4 weeks with dose increases of 1-dose levels at each escalation. If symptoms occur, the dosing symptom rules in the build-up phase would apply
- Missing >7 consecutive days of therapy constitutes an individual stopping rule and the subject would no longer take the study product. The subject will be asked to return to the Clinical Research Center 14 days following their last dose of study product to undergo an Early Discontinuation Visit (see Section 6.5)
- Additionally; excessive missed doses, i.e., > 3 consecutive days missed on 3 occasions, constitutes an individual stopping rule and the subject would no longer take the study product. The subject will be asked to return to the Clinical Research Center 14 days following their last dose of study product to undergo an Early Discontinuation Visit (see Section 6.5).

No attempt should be made to make up for a missed dose if greater than 6 hours have elapsed since usual time of dosing.

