6.12 Visit Windows

Dosing schedule should be adhered to strictly. Two days before, or 2 days after a planned dosing visit, is an acceptable window with continued daily dosing of the current dose level. Study visits for scheduled blood draws or DBPCFC should take place within 2 weeks of the scheduled visit.

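### Protocol 6.8.2 gives two incompatible re-escalation rules for temporary dose reductions lasting more than 3 days

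*Protocol*

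**What the plan says.** The paragraph on temporary reductions in Protocol 6.8.2 covers discretionary cuts, from one step down to about half the current dose, during a respiratory infection, influenza or menses. It contains three rules:

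- **7-day rule.** If the cut is of more than one step, or lasts more than 3 days, "the subject is to return to the CRC within 7 days of the dose-reduction for dose re-escalation under direct observation".
- **Short-cut rule.** "If the reduction in dose is maintained for ≤ 3 days, then the pre-reduction dose may be resumed directly". For one-level cuts of this length, the investigator chooses whether re-escalation happens at home or in the Clinical Research Center (CRC).
- **Hold rule.** "If the reduction in dose is maintained for ≥ 3 days" (sign as printed), the schedule is "reset to maintain the new dose for a 2-week period prior to re-escalating in a bi-weekly stepwise fashion".

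Two general statements on dose reductions lie outside that paragraph. Protocol 6.4.2 says "Subjects who require dosing reduction during the 2-week period will reset their 2-week escalation schedule". Earlier in 6.8.2, subjects needing a reduction "will reset their 2-week escalation schedule to maintain the new dose for a 2-week period prior to attempting to escalate again". Neither mentions the 7-day rule.

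The timing of up-dosing is a secondary objective (Protocol 2.2) but not a listed secondary endpoint (Protocol 3.7). SAP 10.1 serves it by tabulating, by treatment group and every 2 weeks, the number and percent of subjects on each dose, with boxplots and no test.

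**The concern.** A site treating a child with a week of influenza needs one instruction on when to raise the peanut dose again. The protocol gives two, and following either breaks the other. Under Protocol 13 any departure from study procedures is a deviation, so read literally such a case cannot be handled without one.

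About 8 sites are expected (Protocol 6.1), and they may resolve the conflict differently. For the affected subjects, the dose-by-week table would then partly reflect which sentence the site followed rather than what the subject tolerated. The 7-day sentence also does not name the dose to be given at that visit: the full pre-reduction dose, or one level up.

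**Working it through.** **1. Do both rules apply to the same reduction?** The 7-day rule is triggered by more than 3 days and the hold rule by 3 days or more (as printed). Every cut longer than 3 days triggers both, whether the second sign is read as ≥ or >.

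**2. Can both be met?** The reduction ends only when the dose is raised, so the 7 days must run from its start. That puts re-escalation at Day 7 or earlier, and the hold puts it at Day 14 or later. Protocol 6.12 says "Two days before, or 2 days after a planned dosing visit, is an acceptable window". Even if that allowance is applied to both rules, the latest date under one is 7 + 2 = Day 9 and the earliest under the other is 14 − 2 = Day 12. No day satisfies both. Nor can the Day 7 visit be only a check before the hold: the first sentence makes re-escalation its purpose, and the second places the hold before re-escalation.

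**3. How far apart are the readings?** Inputs are the dose ladder of Protocol Tables 3-1 and 3-2 (3, 6, 12, 20, 40, 80, 120, 160, 200, 240, 300 mg) and 14-day steps. For a cut of k levels, the weeks to regain the pre-reduction dose are:

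- A, full dose at Day 7: 1
- B, one level at Day 7, then biweekly: 1 + 2(k − 1)
- C, 2-week hold, then biweekly: 2k

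C − B = 2k − 1 − 2k + 2 = 1 week for every k. Taking half the dose to the nearest ladder level (an assumption):

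| Cut | k | A | B | C |
|---|---|---|---|---|
| Any one-step cut | 1 | 1 | 1 | 2 |
| 120 to 80 or 40 mg | 1–2 | 1 | 1–3 | 2–4 |
| 160 to 80 mg | 2 | 1 | 3 | 4 |
| 200 to 120 or 80 mg | 2–3 | 1 | 3–5 | 4–6 |
| 240 to 120 mg, or 300 to 160 mg | 3 | 1 | 5 | 6 |

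At 80 mg or below, a half-dose cut is one step. The largest gap, 6 − 1 = 5 weeks, needs reading A.

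**4. What would the SAP table show?** Take a 6 mg start, with 240 mg reached on Day 112, and a cut to 120 mg on Day 120.

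- B: 160 mg on Day 127, 200 on 141, 240 on 155, 300 on 169.
- C: 160 mg on Day 134, 200 on 148, 240 on 162, 300 on 176.
- At Week 20 (Day 140) and Week 22 (Day 154), both show 160 and then 200 mg.
- Reading A, with the 2-week clock restarted at Day 127, would show 240 and then 300 mg.

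Whether a 1-week lag appears depends on timing. Move the same cut to Day 115: B reaches 160 mg on Day 122 and 200 mg on Day 136, and C on Days 129 and 143. At Week 18 (Day 126) the entries are 160 and 120 mg, and at Week 20 they are 200 and 160 mg. That is one level apart.

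**5. Week 34.** SAP 3.2.2 gives about 18 or 20 weeks to 300 mg without reductions. The slowest single-cut case is a 3 mg start, 240 mg halved on Day 139, and reading C: 139 + 42 = Day 181 to regain 240 mg, then 14 days to 300 mg on Day 195. That is 195/7 = Week 27.9, about 6 weeks inside the limit if nothing else delays the subject.

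**The case against.** **Sites have guidance.** The general 2-week hold appears in 6.4.2 and again in 6.8.2, and 6.8.2 makes the Medical Monitor available for dosing questions the protocol does not answer. Both may steer sites to the hold, so divergence between sites is an inference. But neither sets precedence. The general rule never mentions the 7-day sentence, and 6.4.2 links the new dose to the severity of dose-related symptoms, so it may not be aimed at cuts for infection or menses. The Medical Monitor is offered for unanswered questions; here the protocol answers twice, so a site following either sentence may see no reason to ask.

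**The difference is small.** This largely stands. A 1-week lag lies within the 1–2 weeks by which any escalation may already be postponed on clinical judgment (6.4.2, 6.8.2). The decision to cut and the size of the cut are also discretionary, so dose by week already mixes tolerance with judgment. The 5-week gap rests on reading A, which is the weaker reading because the paragraph permits direct resumption only after cuts of 3 days or less.

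**Exactly 3 days.** As printed, both the short-cut rule and the hold rule apply to a cut of exactly 3 days. The second sign may be an extraction error, since comparison signs vary elsewhere in this text, so this overlap is only something to confirm.

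**Safety.** A reader might infer that raising the dose by Day 7 is hazardous. The documents do not support that. After 3 or 4 consecutive missed doses, Protocol 6.9 says "The next dose would be the current dose and would be given under observation (Clinical Research Center"), so prompt observed return to the current dose is accepted elsewhere in the plan.

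**Conclusion.** The contradiction is real and is in the current text: for temporary reductions of more than 3 days, Protocol 6.8.2 cannot be followed as written. The consequence is modest. Under stepwise readings the two rules differ by 1 week, which moves an affected subject by at most one level in the biweekly table and in some timings not at all. More than that requires the unstated full-dose reading of the 7-day visit. The affected output is descriptive.

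A reader might go further and infer bias between arms, lost power or extra escalation failures. Both arms follow the same text under blinding, the primary analysis does not use the pace of re-escalation, and a single cut does not by itself reach Week 34. None of these is claimed.

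The conclusion assumes 14-day steps and half-doses taken to the nearest ladder level. It also assumes that Figure 6–2, which is not reproduced in the text available, does not settle the matter; its title concerns the day of symptom, and this paragraph does not cite it. The documents do not say how often such reductions occur, so the overall amount of noise cannot be estimated.

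**What to change.** State one rule in 6.8.2 and delete the 7-day sentence.

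- **Reductions of 3 days or less:** resume the pre-reduction dose directly by the end of Day 3. Do this under observation in the CRC if the cut was more than one step; otherwise at home or in the CRC at the investigator's discretion.
- **Reductions of more than 3 days:** hold the reduced dose for 2 weeks, then re-escalate one step every 2 weeks with the first dose of each step in the CRC. This agrees with the general hold in 6.4.2 and 6.8.2.

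The Day 3 limit matters. If a multi-step short cut kept a 7-day return window, a subject coming back on Days 4 to 7 would already have been reduced for more than 3 days and would fall under the hold.

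Confirm that the second threshold is meant to read > 3 days.

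If the sponsor intended the 7-day rule, delete the 2-week sentence in this paragraph, state the target dose at the visit, and exempt these temporary reductions from the general hold in 6.4.2 and 6.8.2. Deleting the sentence alone would leave that general hold in force.

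The preferred change costs one paragraph of wording and adds no procedures. Its downside is slightly slower re-escalation after longer reductions. The alternative also requires edits to the general statements.
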